**1. Introduction and Purpose:**

Anticoagulation is essential during extracorporeal membrane oxygenation (ECMO) to prevent catastrophic circuit clotting. Use of unfractionated heparin (UFH) as the standard of care during ECMO was adapted from the knowledge gained from cardiopulmonary bypass. Unfortunately, UFH has several limitations during ECMO. Bivalirudin, a direct thrombin inhibitor, is an alternative and potentially superior anticoagulant for patients on ECMO. Previous studies of bivalirudin use during ECMO have shown that compared to UFH, bivalirudin is safe and may decrease bleeding, decrease blood product transfusion, and decrease ECMO cost [1-4]. Improving anticoagulation during ECMO is critically important as the most common complications during ECMO are secondary to bleeding and clotting [5].

We hypothesize that neonatal and pediatric ECMO patients receiving bivalirudin will spend more time at goal anticoagulation and will experience less hemorrhagic and thrombotic complications when compared to patients receiving unfractionated heparin.

Aim 1: Compare the efficacy of bivalirudin versus UFH during neonatal and pediatric ECMO.

Aim 2: Define the incidence of hemorrhagic and thrombotic complications in patients receiving bivalirudin during ECMO.

Aim 3: Determine the optimal dosing for bivalirudin for effective anticoagulation on ECMO.

The primary outcome of the study will be to compare the percentage of time spent at goal anticoagulation for patients receiving UFH versus patients receiving bivalirudin. Secondary outcomes will include incidence of major bleeding events as defined by the International Society of Thrombosis and Hemostasis including fatal bleeding, intracranial hemorrhage, retroperitoneal hemorrhage, extrasurgical or unexpected surgical site bleeding that causes a decrease of hemoglobin of > 2 g/dL or leads to transfusion of two or more red blood cell transfusions within a 24 hour period, and surgical site bleeding that requires surgical intervention [6, 7]. We will compare the need for blood product transfusion of packed red blood cells, platelets, fresh frozen plasma, cryoprecipitate, and antithrombin III (thrombate) between those who received UFH versus those who received bivalirudin. Lastly, we will describe the median dose needed for bivalirudin in all patients and for those with renal insufficiency and renal failure.

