**2. Background:**

Extracorporeal membrane oxygenation (ECMO) is a lifesaving therapy for patients with respiratory and/or cardiac failure. Approximately 1500 to 2000 neonatal and pediatric patients are placed onto extracorporeal membrane oxygenation (ECMO) each year for respiratory failure [8]. At Children's Medical Center, we place approximately 40 neonatal and pediatric patients onto ECMO each year. Despite advancements in ECMO circuit technology such as heparin coated tubing, smaller oxygenators, and improved cannula, hemorrhage and thrombosis are the most common complications during ECMO [8, 9]. Approximately 4-11% of neonatal and pediatric ECMO patients suffer an intracranial hemorrhage and 30% have some form of thrombosis [10, 11]. Hemostatic complications during ECMO are associated

with increased morbidity and mortality [5, 11]. In order to prevent catastrophic circuit clotting, anticoagulation is essential.

As mentioned previously, UFH is currently the standard anticoagulant for ECMO but it has several important limitations. UFH requires antithrombin for maximum therapeutic effect but neonates and critically ill patients are known to be deficient in antithrombin. Besides binding to antithrombin, UFH binds to the ECMO circuit and other plasma proteins altering its pharmacokinetics. The tests used to monitor UFH's clinical effectiveness such as aPTT, ACT and anti-factor Xa are all imperfect tests and have been shown to have variable correlation to themselves and to UFH during ECMO [12-16]. There are no randomized studies that have investigated superiority of UFH over other anticoagulants during ECMO. In addition, there is no universally accepted test or combination of tests to monitor the functional effect of UFH during ECMO.

Bivalirudin is a specific and reversible direct thrombin inhibitor. Bivalirudin binds to both bound free and clot-bound thrombin and unlike UFH it does not require antithrombin. In addition, bivalirudin also has a short half-life of 25 minutes and has low to negligible immunogenic potential. Bivalirudin is currently FDA approved for patients with unstable angina undergoing percutaneous transluminal coronary angioplasty (PTCA), percutaneous coronary intervention (PCI) with use of glycoprotein IIb/IIIa inhibitor, and patients with heparin induced thrombocytopenia undergoing PCI [17]. Bivalirudin is currently used off label for pediatrics.

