### **3. Concise Summary of Project:**

We will prospectively enroll 30 neonatal and pediatric ECMO patients in the Pediatric Intensive Care Unit and Pediatric Cardiovascular Intensive Care Unit at Children's Medical Center, Dallas campus. The patients will be randomized into two arms; one arm will receive unfractionated heparin and the other arm will receive bivalirudin. There will be 15 patients in each arm for a total of 30 patients. We estimate that we will need to consent 50 patients to achieve our goal of 30 enrolled patients. Enrollment and completion of this study will require approximately two years.

After consent is obtained, patients will be randomized into either the unfractionated heparin group or bivalirudin group. The UFH group will be given UFH as is currently standard of care at Children's Medical Center. A bolus of UFH will be given on initiation and the UFH infusion will be titrated throughout the entire ECMO run based on combination testing of anti-factor Xa, aPTT, and thromboelastogram (TEG).

The bivalirudin group will receive an UFH bolus during cannulation and UFH infusion until consent obtained (maximum time of 24 hours) and then transitioned immediately from UFH infusion to bivalirudin infusion. Once initiated, the bivalirudin infusion will be titrated based on aPTT.

Bivalirudin's trade name is ANGIOMAX® and is manufactured by The Medicines Company. Bivalirudin directly inhibits thrombin by binding to the free and clot-bound thrombin. It is stored in a single-dose vial with 250 milligrams of bivalirudin to be reconstituted with sterile water. After reconstitution it may be stored at 2-8°C for up to 24 hours. It is excreted predominantly through proteolysis with 20% cleared renally. Patients with renal insufficiency or failure required a decrease in infusion rate based on creatinine clearance.

ECMO circuit tubing will be collected at time of circuit tubing change or at the end of ECMO. Normally, the used circuit tubing system is discarded in the appropriate biohazard waste container. For this study, will analyze the circuit tubing after it has been removed from the patient. After removal, the circuits will be drained and filled with normal saline (to prevent further clotting) by one of the ECMO team members or one of our study team members. The steps involved are detailed in the paragraphs below and will be covered by study finances and not billed to the patient in any way.

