The cannula with the circuit tubing system attached is cut away from the patient per standard of care and the circuit is drained of blood. The A-V loop (arterial venous) is created using a T-connector (1/4 x 3/8 inch size) and connected to the circuit. A 1 liter bag of normal saline is run through the circuit until the fluid looks clear with the exception of clots, or fibrin strands, already adhering to the tubing. The bridge ports are then capped and the circuit is placed in a biohazard bag.

After removal of the circuit from the patient, the blood will be appropriately drained into a biohazard bag. The circuit will be filled with normal saline and stored in a biohazard bag. The circuit and the biohazard bag will be labeled with the patient study ID and date. There will be no patient identifiers on the circuit, biohazard bag, or shipment label. The biohazard bag will then be stored in a dedicated storage area that is locked with badge-access entrance only. The circuits will be shipped in the red biohazard bags, in a standard FedEx cardboard box (flushed circuits are non-infectious), with the appropriate shipping label for shipment to Biotechnology Building (IBB) at the Georgia Institute of Technology. The individual responsible for receiving the study circuits is [name].

For the primary outcome, all aPTT and anti-factor Xa values (for the UFH group only) will be recorded during the ECMO run. Hemorrhagic complications will be defined using the International Society of Thrombosis and Hemostasis major bleeding criteria. Blood product transfusion will be recorded in ml/kilogram/ECMO day. Thrombosis will be defined as need for circuit change and clot burden in the ECMO circuit. A clot burden score will be performed on each patient every 6 hours. ECMO cost will include cost of the circuit, cost of blood products including antithrombin, cost of circuit change, and cost of anticoagulant.

Patients in the UFH arm may cross over into the bivalirudin arm if they develop heparin induced thrombocytopenia or heparin resistance defined as UFH dose of > 70 u/kg/hour with inability to obtain goal Xa or aPTT. Bivalirudin patients may cross over into the UFH arm if they are unable to achieve adequate anticoagulation and have continued development of thrombosis in the circuit or the patient or if the patient develops an intracardiac thrombus. The primary team or parent/guardian can withdraw the patient from the study for any reason at any time.

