#### **4. Study Procedures:**

##### Unfractionated heparin group:

Patients in this group will receive UFH anticoagulation as is current standard of care at Children's. During cannulation a bolus dose of 50-100 units/kg of intravenous UFH will be given. A continuous UFH infusion based on age will be initiated once ACT is < 300 seconds. Infants less than one year will receive a starting dose of 28 units/kg/hour and children > 1 year will receive a starting dose of 20 units/kg/hour per current Children's protocol.

The UFH infusion will be titrated based on targeted anti-factor Xa, aPTT, and thromboelastogram. Labs will be drawn per current standard of care as noted below.

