Patients in the UFH arm may cross over into the bivalirudin arm if they develop heparin induced thrombocytopenia or heparin resistance defined as UFH dose of > 70 u/kg/hour with inability to obtain goal Xa or aPTT. Bivalirudin patients may cross over into the UFH arm if they are unable to achieve adequate anticoagulation and have continued development of thrombosis in the circuit or the patient or if the patient develops an intracardiac thrombus.

Randomization:

Patients will be randomized 50/50 into the bivalirudin group or the heparin group. Each group will have 15 patients for a total of 30 patients. Randomization will occur via a sealed envelope assignment.

Research related costs:

Version 1.3 13JUN2018

Thrombin generation assay will be performed on day one and on day three for patients in both arms. The patients will not be responsible for the cost of the test. In addition, per current standard of care at Children's echocardiograms will be performed at time of cannulation and as needed to evaluate cardiac function and/or cannula position. If an echocardiogram is performed on patients in the bivalirudin arm to evaluate for intracardiac thrombus, the patient will not be responsible for the charge.

Patients will be responsible for all standard ECMO related costs including blood product transfusion and anticoagulant. The average wholesale price of bivalirudin for a 250mg vial is \$609. On average one vial per day will be used per patient. The average wholesale price of unfractionated heparin for a 250ml bag is \$20. The entire bag or portion of bag will be used per day per each patient. Therefore, the patients in the bivalirudin arm may incur a higher cost.

Data will be collected on the patients from time of ECMO cannulation to time of hospital discharge. Blood draws for the both groups of patients will follow current CMC protocol for ECMO except that bivalirudin patients will not get anti-factor Xa testing. The only additional test will be a thrombin generation assays. Thrombin generation assays will require an extra 5.4 ml total of blood. In addition, blood samples for dilute thrombin time, ecarin chromogenic assay, bivalirudin level and aPTT will be frozen and stored for future analysis after study completion. Samples will be drawn daily, and obtained from leftover SOC coagulation labs drawn per protocol so no additional blood sampling will be required. Patients will not be responsible for the cost of this analysis.

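### The thrombosis definition omits patient and intracardiac clots that can end bivalirudin treatment, and no analysis set is named although UFH patients may switch for missing goal, the primary outcome.

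*Combined protocol and SAP*

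**What the plan says.** - **Thrombosis.** Section 3 gives the only definition: "Thrombosis will be defined as need for circuit change and clot burden in the ECMO circuit". Section 14 also lists clotting events among the outcomes, without defining them.
- **Leaving UFH.** Sections 3 and 4 allow a switch for heparin-induced thrombocytopenia or for "heparin resistance defined as UFH dose of > 70 u/kg/hour with inability to obtain goal Xa or aPTT".
- **Leaving bivalirudin.** The same sections allow a switch for patients who are "unable to achieve adequate anticoagulation and have continued development of thrombosis in the circuit or the patient", or for an intracardiac thrombus alone. Section 10 words the switch after intracardiac thrombus as definite.
- **Primary outcome.** Section 1 makes it the percentage of time at goal anticoagulation.
- **Analysis.** Section 14 lists tests and outcomes. Neither it nor any other section supplied names an analysis set or says how time and events after a switch are counted.
- **Wording of the comparison.** Section 1 words the transfusion comparison as "between those who received UFH versus those who received bivalirudin". Section 3 uses the same verb for the allocated groups: "one arm will receive unfractionated heparin and the other arm will receive bivalirudin".
- **Monitoring.** For the primary outcome, "all aPTT and anti-factor Xa values (for the UFH group only) will be recorded during the ECMO run". Section 4 (Research related costs) says bivalirudin patients are not tested for anti-factor Xa.

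**The concern.** There are two linked problems.

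The first is in a stated rule. A thrombus in the heart or elsewhere in the patient is serious enough to end bivalirudin treatment, yet the circuit-only definition does not count it. The study hypothesises fewer thrombotic complications on bivalirudin, and Aim 2 sets out to define their incidence on that drug. A literal reading would leave out the very clots the protocol treats as decisive at the bedside.

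The second is selection. Poor control alone, at a high dose, can move a UFH patient; a bivalirudin patient needs poor control plus continuing thrombosis, or an intracardiac thrombus. Except for heparin-induced thrombocytopenia, which is not a listed outcome, leaving therefore depends on the primary outcome or on thrombosis. With 15 patients per arm and no rule in section 14, the handling of switchers could be chosen once it is known who switched. Two of the options, dropping them or counting them by drug received, lose the randomised comparison.

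**Working it through.** The documents give no switch rate and no spread for time at goal, so there is no figure of the plan's own to reproduce here. What follows is an illustration on stated assumptions.

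**Time at goal, two equal drugs.** From the plan: 15 per arm. Assumed: failing patients are at goal b = 20% of the time and others g = 60%; k = 1 to 4 failing patients per arm, f = k/15; UFH failures switch at a fraction t = 0.25 to 0.5 of the run; control after the switch c = 20 to 60%; a share s = 0 to 1 of bivalirudin failures also leave.

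The true drug difference is zero. The largest apparent UFH-minus-bivalirudin gaps for k = 1 occur at s = 0 and t = 0.25:

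- *Randomised arm, all time kept:* f(1−t)(c−b) = (1/15)(0.75)(60−20) = 2.0.
- *Switchers excluded:* 60 − [(14/15)(60) + (1/15)(20)] = 60 − 57.3 = 2.7.
- *Drug received, pooled hours, c = 20:* UFH [(14/15)(60) + (1/15)(0.25)(20)] / [14/15 + (1/15)(0.25)] = 56.33/0.95 = 59.3. Bivalirudin [(14/15)(60) + (1/15)(20) + (1/15)(0.75)(20)] / [1 + (1/15)(0.75)] = 58.33/1.05 = 55.6. Gap 3.7.
- *Post-switch time scored as not at goal:* −f(1−t)b = −(1/15)(0.75)(20) = −1.0.
- *Per-patient time up to the switch:* 0, because control is assumed constant within a patient.

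Over the whole grid:

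| Rule | k = 1 | k = 4 |
|---|---|---|
| Randomised arm | 0 to +2.0 | 0 to +8.0 |
| Switchers excluded | 0 to +2.7 | 0 to +10.7 |
| Drug received | 0 to +3.7 | 0 to +12.2 |
| Post-switch scored as not at goal | −1.0 to 0 | −4.0 to 0 |
| Per-patient, up to switch | 0 | 0 |

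These signs are a product of the set-up, in which bivalirudin exits never outnumber UFH exits. Interchanging the arms (one bivalirudin exit, no UFH exit) gives −2.0 by randomised arm, −2.7 with the switcher excluded and −3.7 by drug received. The sizes are informative; the direction is not.

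No rule is neutral in every setting. If failing patients go from 20% in the first half of the run to 60% in the second whether or not they switch (t = 0.5, s = 0), time up to the switch gives f(20−40) = −1.3 for k = 1 and −5.3 for k = 4, while the randomised-arm rule gives f(40−40) = 0.

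The heparin-resistance threshold is 70/28 = 2.5 to 70/20 = 3.5 times the starting doses in section 4, so one switch may be nearer the truth than four.

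**Thrombosis.** Section 2 says that "30% have some form of thrombosis". Taken as a yes/no event, that is 4 or 5 of 15 in each arm. Suppose bivalirudin patients leave for a clot and no UFH patient leaves (UFH minus bivalirudin, points):

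- *One exit:* randomised arm 0; excluded 4/15 − 3/14 = 5.2 or 5/15 − 4/14 = 4.8; counted in the arm entered 5/16 − 3/14 = 9.8 or 6/16 − 4/14 = 8.9.
- *Two exits:* randomised arm 0; excluded 4/15 − 2/13 = 11.3 or 5/15 − 3/13 = 10.3; counted in the arm entered 6/17 − 2/13 = 19.9 or 7/17 − 3/13 = 18.1.
- *One clot left out by the definition:* 1/15 = 6.7 points in its arm, and 0 if that patient also has a circuit event or if the clot is counted as a clotting event.

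Fisher's exact test on the two largest contrasts (6/17 v 2/13 and 7/17 v 3/13) gives p = 0.41 and 0.44.

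**The case against.** The strongest reply is that much of this is sound design with some detail missing. Exit rules differ because the drugs differ: heparin-induced thrombocytopenia is a complication of heparin, and section 10 links stagnant flow to a thrombus risk on bivalirudin. That is right, and the exit rules are not the fault. Section 4 also collects data from cannulation through to discharge with no stop at a switch, so a comparison by randomised arm can be run on the data as planned. Section 13 calls the study a pilot. On its own, the unnamed analysis set is therefore close to missing detail; it matters because one exit rule acts on the primary outcome. The circuit-only definition is different, since it is a stated rule that leaves events out.

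The model is also crude. The 30% covers any form of thrombosis, not circuit thrombosis, and section 3 includes a clot burden score every 6 hours, which is not a yes/no event. With an assumed SD of 20 points, the standard error at 15 per arm is 20 × √(2/15) = 7.3, so one switch moves time at goal by about half a standard error at most. These limits stand.

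Four stronger readings are tempting, and the documents do not support them:

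- *The plan is as-treated.* The wording in section 1 leaves this open, but section 3 uses the same verb for the randomised arms.
- *The omission favours bivalirudin.* It lowers the count in whichever arm has the clots. Section 10 calls the added risk on bivalirudin theoretical.
- *A switch or two would overturn the conclusion.* The estimate moves, but the thrombosis contrasts stay far from significance. For time at goal, a null simulation (mean 50, SD 20) in which the single worst UFH patient switches gives type I error of 6.8% with that patient excluded and 8.4% if counted as bivalirudin. That is an extreme selection.
- *Time on UFH after a switch cannot be scored.* A patient who crosses into the UFH arm may well get its routine anti-factor Xa and aPTT monitoring, and aPTT is recorded in everyone. The text is unclear on anti-factor Xa but does not rule it out.

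**Conclusion.** The point holds in a limited form. Read literally, section 3 undercounts thrombotic complications by leaving out patient and intracardiac thrombus, and the undefined clotting events in section 14 do not settle whether these count. Exit from UFH can depend on the primary outcome while section 14 fixes no analysis set, so an analysis that drops switchers or counts them by drug would not compare randomised groups.

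The real size is unknown because no switch rate is given. On the assumed values, one failing patient per arm shifts time at goal by up to about 4 points, in a direction set by which arm switches more. An omitted clot is 6.7 points in its arm only if that patient has no circuit event. The absence of a numeric UFH goal affects every UFH patient, switched or not, and is a separate matter. This should be corrected, but it does not invalidate the design.

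**What to change.** Leave the clinical exit rules as they are.

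1. **Section 3, thrombosis.** Add intracardiac and other patient thrombus to circuit change and circuit clot burden, in both arms. Count every event, including one that triggers a switch, in the randomised arm. Report by arm the number of echocardiograms done for suspected thrombus, without requiring more.
2. **Section 14, analysis.** Make the primary comparison by randomised arm, with post-switch time kept and scored against the goal of the drug being infused. Describe it as a comparison of strategies that include their exit rules. Report per-patient percentage of time at goal up to the switch as a sensitivity analysis, with the number, time and reason of switches by arm.
3. **Section 4, monitoring.** State that bivalirudin-arm patients switched to UFH have anti-factor Xa recorded on the UFH schedule.

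**Cost.** Text edits, and a switch time and reason on the data sheet. Anti-factor Xa every 6 hours once at goal is 24/6 = 4 draws a day, only in patients who switch to UFH, and is the site's usual monitoring for that drug.

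**Downsides.** If many patients switch, the randomised-arm estimate may not show the pure drug difference, and time at goal then mixes two yardsticks within one patient. Unequal use of echocardiograms may detect more clots on bivalirudin, which is why their number should be reported by arm.

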#### **5. Sub-Study Procedures:**

None

#### **6. Criteria for Inclusion of Subjects:**

All patients aged 0 days to less than 18 years that require venovenous or venoarterial ECMO in the Pediatric Intensive Care Unit and Pediatric Cardiovascular Intensive Care Unit at Children's Medical Center, Dallas campus.

#### **7. Criteria for Exclusion of Subjects:**

Exclusion criteria will include:

- 1) Patients with known or suspected heparin induced thrombocytopenia prior to consent
- 2) Patients with aPTT > 2 times normal with AST and or ALT > 500
- 3) Patients with plan to decannulate from ECMO within 48 hours
- 4) Known or suspected pregnant women
- 5) Previous enrollment in this study
- 6) Primary language spoken that is not English or Spanish
- 7) Patients with congenital diaphragmatic hernia since this small subgroup of patients are receiving surgical repair while on ECMO and if they were in the Bivalirudin group would need to have the Bivalirudin suspended during and after the surgical procedure. Since the study team is not aware of any published data to suggest how long to hold Bivalirudin for this particular operation, this population is excluded due to safety concerns.

